4.4. Dose Selection Rationale

As described in [Section 1.3.2](#), data suggest that doses up to 1500 mg/day of other formulations of cannabidiol may be safe. These dose levels were selected based on data regarding concentrations that have been administered with other cannabidiol products without significant safety concerns and accounting for the range of body weights of patients to be enrolled in this study.

Additionally, doses up to 40 mg/kg/day were administered by the Sponsor in studies [INS011-14-029](#) and [INS011-14-030](#) and were generally well tolerated. Three infants were dosed initially with 40 mg/kg/day in [INS011-14-029](#) and continued on the same dose in [INS011-14-030](#), which was a 48-week, long-term safety study. Two of four infants who received 20 mg/kg/day in [INS011-14-029](#) titrated their dose from 20 mg/kg/day up to 40 mg/kg/day and continued receiving this dose throughout the long-term safety study. No infants had dose reductions in [INS011-14-029](#), [INS011-14-030](#), or [INS011-15-054](#), the double refractory infantile spasms study. Thus, whether the dose was provided with or without titration, all infants generally tolerated the 40 mg/kg/day dose. Thus, these same doses will be administered in this study.

4.5. Selection and Timing of Dose for Each Patient

Patients will receive vigabatrin and CBD or CBD Placebo twice daily during the 15-day Initial Treatment Period as described in [Section 4.1](#). Subsequently, Complete Responders will receive CBD or CBD Placebo and/or vigabatrin twice daily during the 75-day Extended Treatment Period.

The date and time of all investigational product administrations will be documented in the case report form (CRF).

4.6. Treatment Compliance

The doses of vigabatrin and CBD or matching placebo will be administered at the study center on the days listed in [Table 1](#) under the supervision of the investigator (or a designee). All other doses will be administered by a parent or caregiver.

The Investigator, a member of the investigational staff, or a hospital pharmacist must maintain an adequate record of the receipt and distribution of all study medication using the Drug Accountability Form. These forms must be available for inspection at any time.

All supplies of IP should be accounted for at the termination of the study and a written explanation provided for any discrepancies. All unused supplies and packaging materials are to be inventoried and returned by the Investigator to the Sponsor or a designee. The Investigator is not permitted to return or destroy unused clinical drug supplies or packaging materials unless authorized by the Sponsor or a designee.

If the study is terminated, discontinued, suspended, or completed, all unused supplies of the investigational product will be returned to the Sponsor or a designee for destruction after the final drug accountability check has been performed. Sponsor approval is required prior to drug destruction. A certificate of destruction will be provided to the Sponsor.

All regulations issued by the DEA or per local regulations in ex-US locations concerning the accountability of Schedule I medications will be followed (e.g., prevention of diversion).

4.7. Permitted and Prohibited Therapies

4.7.1. Permitted Therapies

Any medications (other than those excluded by the protocol, see Section 4.7.2) that the investigator considers necessary for a patient's welfare and will not interfere with the investigational product may be given at the Investigator's discretion.

4.7.2. Prohibited Therapies

During the Screening, Initial Treatment, Extended Treatment, Taper, and Follow-up Periods, patients are not to receive the following:

- Any cannabinoids besides the investigational drug (other formulations of CBD, Δ^9 -THC, hemp oil, Realm Oil or marijuana). Exclusion criterion number 4 prohibits use within 30 days of study entry.
- Felbamate.
- Valproic acid.
- Clobazam.
- Corticotrophins.
- Medication(s) that are strong CYP3A4 inhibitors or inducers or CYP3A4-sensitive substrates with a narrow therapeutic index. A list of these medications is provided in [Appendix 1](#).
- Systemic steroid therapy (excluding inhaled medication for asthma treatment).
- Any other investigational drug or investigational device.
- Introduction of new anti-epileptic therapies (AETs) during the study is prohibited.

Patients must refrain from consumption of grapefruit, grapefruit juice, Seville oranges, Seville orange marmalade, or other products containing grapefruit or Seville oranges within 3 days of the first administration of investigational product and throughout the entire Treatment and Taper Periods.

Although they are not prohibited, patients taking concomitant medications may need to be monitored with special care to identify any AEs arising due to the potential for altered drug metabolism. This is discussed in detail in [Section 6.2.6.9](#).

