1.4. Infantile Spasms

Infantile Spasms is a devastating form of epilepsy that typically strikes children in the first year of life.⁶² Usually provoked by one of many structural, genetic, or metabolic etiologies, Infantile Spasms manifests with clusters of a distinct seizure-type (spasms), and is often accompanied by an EEG pattern known as hypsarrhythmia.⁶³ Unsuccessful treatment, as well as delay in definitive treatment, are associated with tremendous reductions in neurodevelopmental outcome.⁶⁴ Among pharmacologic therapies for infantile spasms, hormonal therapies such as intramuscular adrenocorticotrophic hormone (ACTH, Acthar[®])^{65,66,67} and vigabatrin (Sabril[®])⁶⁸ are the most efficacious. Almost half of patients either fail first line therapy or relapse after initially successful treatment.⁶⁹ The side-effect profiles of the above therapies are poor: vigabatrin is associated with irreversible peripheral visual field defects^{70,71} and the hormonal therapies impart substantial risk of immunosuppression leading to potentially lethal bacterial infections (pneumonia, sepsis, meningitis, etc.) as well as hypertension that has been associated with cardiac failure.

Accordingly, there is a tremendous need for safe and effective therapies in the treatment of infantile spasms. This need is even more pronounced in those patients who have failed currently approved therapies.

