3.1.4. Taper Period

Following the completion of the Initial Treatment Period (Visit 6), partial responders who do not enroll in the open-label safety study and non-responders will have vigabatrin and CBD tapered as follows:

- Vigabatrin taper: 150 mg/kg/day will be reduced to 100 mg/kg/day for 3 days, then the 100 mg/kg/day dose will be reduced to 50 mg/kg/day for 3 days, and then discontinued.
- CBD or CBD Placebo taper: 40 mg/kg/day will be reduced to 30 mg/kg/day for three days, then 30 mg/kg/day will be reduced to 20 mg/kg/day for 3 days, and then discontinued.

Complete Responders will be tapered off vigabatrin and CBD or CBD placebo at the completion of the Extended Treatment Period, and all patients will be tapered off at any Early Withdrawal Visits, using the same schedules as described above.

[figure not shown]
If the investigator decides to continue vigabatrin as a treatment for patients after the end of study or early withdrawal, tapering of vigabatrin will be left to the discretion of the PI.

CBD requires tapering off at the End of Study or at the Early Withdrawal visit.

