3.1.5. Follow-up Period

A follow-up phone call will occur for all subjects 30 days after discontinuation of the study drug to assess AEs, AETs, and record concomitant medications.

Figure 1: Study Design Schematic

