7.2.6. Follow-up Period

A follow-up phone call will occur for all subjects 30 days after discontinuation of the study drug to assess AEs, AETs, and record concomitant medications.

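### Section 4.7.2 carries the ban on corticotrophins, systemic steroids and new anti-epileptic therapies through Taper and Follow-up with no exception for non-response or relapse: as written, 34 to 36 days from the start of taper for infants whose primary endpoint is already complete

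*Protocol*

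**What the plan says.** Protocol section 4.7.2 sets the span of its prohibitions in one lead-in: "During the Screening, Initial Treatment, Extended Treatment, Taper, and Follow-up Periods, patients are not to receive the following". Among the items are corticotrophins (no qualifier), systemic steroids (only inhaled asthma medication is exempt) and new AETs, the last worded "Introduction of new anti-epileptic therapies (AETs) during the study is prohibited".

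Section 4.7.1 lets the investigator give what the patient's welfare requires, but begins "Any medications (other than those excluded by the protocol, see Section 4.7.2", so that discretion does not reach the listed drugs.

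After the Day 15 assessment, section 3.1.4 provides that partial responders who do not join the open-label study and "non-responders will have vigabatrin and CBD tapered as follows". The same section contains one relaxation, beginning "If the investigator decides to continue vigabatrin as a treatment for patients after the end of study or early withdrawal", under which the vigabatrin taper is left to the investigator. Section 3.1.5 then says "A follow-up phone call will occur for all subjects 30 days after discontinuation of the study drug", and section 7.2.6 gives the purpose of that call: "to assess AEs, AETs, and record concomitant medications".

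For a complete responder who is reported to relapse, section 7.2.3 provides a confirmatory 9-hour video EEG. It names no therapy to follow.

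**The concern.** Section 1.4 of the protocol names two efficacious options for infantile spasms: hormonal therapy such as ACTH, and vigabatrin. It also warns: "Unsuccessful treatment, as well as delay in definitive treatment, are associated with tremendous reductions in neurodevelopmental outcome". A non-responder at Day 15 has vigabatrin tapered by default, while 4.7.2 read literally withholds the other named class until the follow-up call.

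The trial gains little efficacy information in return. The primary endpoint (8.1.1) is read at Day 14-15, and no efficacy endpoint in 8.1.2 uses data from these infants after Day 15. A site that follows the period list could hold back another therapy from an infant with continuing spasms, and sites could read the list differently. Partial responders can enter an open-label study that allows standard-of-care treatment with CBD (3.1.3); non-responders are offered no equivalent.

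**Working it through.** **1. The plan's own total.** Section 3.1 gives a maximum duration of about 140 days over five periods. Inputs: screening 14 days (3.1), treatment to Day 90 (3.1.2), taper 3 + 3 = 6 days (3.1.4), follow-up 30 days (3.1.5).

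14 + 90 + 6 + 30 = 140.

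The total reproduces, so Follow-up is counted as part of the study. With the 4-week call in footnote j of the Schedule of Events the total is 14 + 90 + 6 + 28 = 138, which also fits.

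**2. Length of the ban from the start of taper.**

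- Footnote j: 6 + 28 = 34 days.
- Sections 3.1.5 and 7.2.6: 6 + 30 = 36 days.

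The count from Day 15 is longer, because all infants stay on treatment until the central EEG reading arrives. If that wait used the whole 5-day allowance on Visit 6 (my assumption), the upper figure would be 36 + 5 = 41 days. If vigabatrin is continued, the 6-day taper applies only to CBD or placebo. SAP section 4 has a 3-day taper and 30±7 days of follow-up (3 + 30 = 33; range 26 to 40). The SAP was written for protocol version 2.0 and describes a different design, so the protocol's lengths are used.

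**3. Does each item run on after Day 15?**

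- Corticotrophins and systemic steroids: yes. Nothing in either item limits the lead-in. The grapefruit restriction in the same section stops at the end of Taper, so the section does set different end points when it means to.
- New AETs: ambiguous. The item is tied to the study, and footnote b puts End of Study assessments at Day 15 for partial and non-responders. Against that, section 3.1 counts Follow-up as one of the study's five periods. Recording AETs at the call is not permission to start one.

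**4. Does any other provision release the infant?**

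- Continuing vigabatrin (3.1.4) keeps the current drug; it does not allow a new one.
- Withdrawal by the family, or discontinuation by the investigator or sponsor for welfare (3.3), ends participation. Taper and the follow-up call still apply afterwards, so it is unclear whether the ban still binds.
- A deviation under 9.8 requires an immediate hazard and may lead to withdrawal.
- The open-label study (3.1.3) is for partial responders only.

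**5. How many infants.** Inputs: 60 placebo and 130 CBD patients, response rates 40% and 60% (8.2).

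- Planning rates: 60 × 0.60 = 36; 130 × 0.40 = 52; 36 + 52 = 88; 88/190 = 46%.
- 40% in both arms: 36 + 130 × 0.60 = 36 + 78 = 114; 114/190 = 60%.

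Both counts include partial responders, some of whom will enter the open-label study. The documents do not give the partial/non-response split, a relapse rate, or the time at which a relapsed infant starts taper.

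**The case against.** The best reply is that this is loose drafting and not an intended rule. The AET item is tied to the study, End of Study is Day 15 for these infants, vigabatrin may be continued, and AETs are recorded at the call; together these suggest that care was meant to return to the treating clinician. Families may leave at any time without loss of benefits (3.3, 10.4), and withdrawal need not cost the infant safety follow-up, since 3.3 still follows adverse events and the call covers all subjects. This stands for the AET item and narrows the practical harm. It does not remove the problem: the corticotrophin and steroid items have no such limit, and leaving the trial should not be the route to next-line treatment.

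A second objection also stands. Lifting the steroid and ACTH ban at the Day 14-15 result could put an infant on hormonal therapy while still taking CBD. Section 1.6 lists possible downregulation of immune responses as a CBD concern, and section 1.4 describes serious infection risk from immunosuppression with hormonal therapy. The documents do not settle whether the overlap is acceptable.

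A reader might infer that some 88 infants will go untreated for five weeks. The documents do not support that. The figure is an expected count of infants without complete response under the sponsor's assumptions, neither an upper bound nor an estimate of those affected, and no passage shows that sites will withhold treatment.

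**Conclusion.** The point holds as a rule on the page with a possible cost to patients. As written, corticotrophins and systemic steroids, and on one reading new AETs, are barred for 34 to 36 days after taper starts in non-responders and in partial responders outside the open-label study. The same list gives a relapsed infant no exception, but that duration cannot be computed. The existing reliefs are partial: none clearly lets an infant who stays in follow-up start another therapy.

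The length rests on the protocol's taper and follow-up periods. The expected number without complete response (88 of 190, or 114 of 190 with no CBD benefit) rests on the response assumptions in 8.2, and the number affected is smaller by an unknown amount. It would be wrong to infer that the efficacy comparison is biased: the restriction at issue falls after these infants' efficacy endpoints have been read, and for relapse after the event has been confirmed. It should be fixed; confidence is medium because the intended scope of the AET item is unclear.

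**What to change.** Amend 4.7.2 so that the ban on corticotrophins, systemic steroids and new AETs ends for a patient at the earliest of:

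- (a) a Day 14-15 result that is not a complete response, including a missing EEG counted as non-response under 8.4.6;
- (b) EEG-confirmed relapse;
- (c) early withdrawal, once the withdrawal assessments are done.

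Keep the ban for complete responders in Extended Treatment who have not relapsed. Keep the cannabinoid and CYP3A4-interaction restrictions, including the AETs in Appendix 1, at least through the CBD taper. The sponsor's clinicians should set when those restrictions, and the separate felbamate and clobazam bans, end. They should also decide whether steroids or ACTH may overlap with CBD or must wait until it is stopped. State that the follow-up call and adverse event collection continue after a new therapy starts. Which therapy to use is not for this review to say.

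This is a cheap improvement: amendment wording, with no visit, assessment or efficacy endpoint changed. It has two downsides. Adverse events are collected to 30 days after the last dose (7.2.7), so some follow-up events may be confounded by the new therapy, although the call already records AETs and concomitant medications. The possible overlap of steroids or ACTH with CBD also needs a clinical ruling before the wording is final.

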5. STUDY DRUG MATERIALS AND MANAGEMENT

5.1. Identity of Investigational Product

The active pharmaceutical ingredient (API) in Cannabidiol Oral Solution is a pharmaceutical-grade synthetic cannabidiol manufactured according to cGMP. It is an off-white to pale yellow resin or crystal substance that is soluble in several organic solvents with an acid dissociation constant (pKa) of 9.64. The solution is a clear, colorless to pale yellow to brown colored solution filled into a 30-mL amber glass bottle. More detailed information may be found in the IB.

5.2. Labeling and Packaging

5.2.1. Labeling

The labels for the investigational product will contain all information according to regulatory requirements.

5.2.2. Packaging

A description of the drug products may be found in Table 3. The investigational product will be supplied in 30 mL containers of a 100 mg/mL strength (i.e., 3000 mg per container).

Table 3: Description of Drug Product (20 mg/kg/day, 30 mg/kg/day, 40 mg/kg/day)

Non-proprietary or common name of drug product	Cannabidiol Oral Solution, 100 mg/mL
Dosage form	Oral solution
Strength	100 mg/mL

The investigational product will be clearly marked according to FDA and/or ICH requirements regarding use for clinical study investigation only and will be labeled with the investigational product name, study reference number, and storage conditions. It is the responsibility of the Investigator to ensure that accurate accountability records are maintained throughout the study. Study center staff will dispense the investigational product according to the handling instructions.

5.3. Dispensing and Storage

The investigational product will be stored at a controlled room temperature (20 to 25 degrees Celsius, 68 to 77 degrees Fahrenheit) or refrigerated (2 to 8 degrees Celsius, 36 to 46 degrees Fahrenheit) at the study center.

The investigational product will be dispensed from a Schedule I licensed study center. Ex- US centers must meet local regulations for dispensing investigational product. The investigator will provide study medication and exact dosing instructions to parent(s)/caregiver(s) for titration doses during Visits 2 and 3 and the full Initial Treatment Period doses during Visit 4 to be administered at home. Drug for the extended treatment period will be dispensed after clinical laboratory results and 24-hour video EEG readings have been received. Study drug will be stored at room temperature.

Cannabis and its constituents (including cannabidiol) are Schedule I controlled substances in the United States and subject to all applicable local and federal laws and regulations regarding these products. This includes security provisions for storing the controlled substances and for dispensing in a manner to prevent diversion. Additionally, the Sponsor or Investigator must provide a statement of the quantity to be manufactured and the sources of the chemicals to be used or the substance.

For US sites, the DEA regulations detail specific security requirements for storage of the investigational product. For ex-US sites, local regulations must be adhered to and IP must be securely locked in a substantially constructed cabinet. Any loss in investigational product must be reported to the Sponsor. Licensed practitioners must store controlled substances in a “securely locked, substantially constructed cabinet” and must notify the DEA of the theft or significant loss of any controlled substances within 1 business day of discovering such loss or theft. Furthermore, all practitioners are prohibited from hiring employees who have been convicted of a drug-related felony or who have had a DEA registration denied or revoked.

Investigators are responsible for ensuring that all applicable licensures are in place and storage conditions are appropriate.

Study centers are required to provide complete information, including CRFs and final outcomes, on all instances of addiction, abuse, misuse, overdose, drug diversion/drug accountability, discrepancies in the amount of the clinical supplies of the investigational product, noncompliance, protocol violations, lack of efficacy, individuals lost to follow-up, and any other reasons why patients dropped out of the study.

5.4. Drug Accountability

The Investigator, a member of the investigational staff, or a hospital pharmacist must maintain an adequate record of the receipt and distribution of all study medication using the Drug Accountability Form. These forms must be available for inspection at any time.

All supplies of IP should be accounted for at the termination of the study and a written explanation provided for discrepancies. All unused supplies and packaging materials are to be inventoried and returned to the Sponsor or a designee by the Investigator. The Investigator is not permitted to return or destroy unused clinical drug supplies or packaging materials unless authorized by the Sponsor or a designee.

If the study is terminated, discontinued, suspended, or completed, all unused supplies of the investigational product will be returned to the Sponsor or a designee for destruction after the final drug accountability check has been performed. Sponsor approval is required prior to drug destruction. A certificate of destruction will be provided to the Sponsor.

All regulations issued by the DEA concerning the accountability of Schedule I medications will be followed (e.g., prevention of diversion). Ex- US centers will be required to follow local regulations.

6. STUDY ASSESSMENTS

6.1. Efficacy Assessments

To assess the efficacy of Cannabidiol Oral Solution, a 9-hour video-EEG will be completed during Screening and a 24-hour video-EEG will be performed from Day 14 (Visit 5) to Day 15. During the Extended Treatment Period, a 9-hour video-EEG will be completed to confirm parent/caregiver reports of relapse or complete resolution. If possible, a 9-hour video EEG will be conducted for patients who have continued into the Extended Treatment Period and decided to Early Withdraw. A video EEG is not required for patients who decide to withdraw during the Initial Treatment Period.

The video EEGs should include at least one full wake/sleep cycle. Video EEGs may be first read by the investigator. However, no efficacy assessment will be made based on the investigator's reading of the video EEG and this read will not be captured in the database. An Independent Central Reader will evaluate all video EEGs in a blinded manner and determine responder status for the primary endpoint. Details regarding requirements for the conduction of the video EEG and the Independent Central Reader's review and assessment of the video EEG is outlined in the EEG Charter. The treatment response categories are summarized in [Table 2](#).

- The CGI-S will be completed by the investigator at screening.
- The CGI-I will be completed by the investigator at Visit 6 of the Initial Treatment Period, or the Early Withdrawal Visit.
- Daily seizure diaries will be completed throughout the Initial and Extended Treatment Periods, or the Early Withdrawal Visit.

If a patient discontinues the study prematurely, the investigator's impression of efficacy and tolerability of the study drug, as evaluated by CGI-I, will be assessed and recorded immediately before discontinuation. If possible, the parent/caregiver will be encouraged to have the patient have an Early Withdrawal video-EEG completed.

